Endpoints:	
Primary:
 
 Incidence and severity of AEs and Adverse Events of interest (urinary retention, withdrawal symptoms) over the course of the study. Adverse Events of special psychiatry interest (nervousness, anxiety, panic attacks, insomnia, aggression, mania, suicidal ideation, development/worsening of depression) over the course of the study Suicidal Adverse Events and Adverse Events suggestive of abuse potential (described in Section 6.2.2.3) will be analysed, and detailed narratives provided Haematology, chemistry, and urinalysis Actual change from end of the Screening Placebo Run-In Period in ECG readings and Week 8. ECG parameters of interest include: ventricular rate, QT interval, corrected QT interval, PR interval, and QRS duration Actual change from end of the Screening Placebo Run-In Period to each visit in standardised cuff systolic and diastolic blood pressure and radial heart rate 
Secondary:
 
The following Efficacy endpoints will be explored

	
 Percentage change from end of the Screening Placebo Run-In Period to Week 8 in the number of incontinence episodes/24 hours Absolute change from end of the Screening Placebo Run-In Period to Week 8 in the number of incontinence episodes/24 hours Proportion of subjects who become continent at Week 8 Change from end of the Screening Placebo Run-In Period in the number of incontinence pads used per week

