 - c. Subjects with current (within 2 years) urogenital neoplasms or malignancies including bladder, uterine or cervical cancer (not applicable to male subjects with prostate cancer in whom a prostatectomy has been performed)
 - d. Subjects with neuropathology that could affect the lower urinary tract or nerve supply, including but not limited to multiple sclerosis, stroke, Parkinsonism, or spinal cord injury
 - e. Subjects with diabetes insipidus
 - f. Clinically significant or unstable, endocrine, hepatic, renal, immunologic, or lung disease (ie, active chronic obstructive pulmonary disease), or malignancy other than non-melanomatous skin cancer
21. Severe renal impairment (estimated glomerular filtration rate < 30 mL/min/1.73m²)
22. Severe hepatic impairment (Child-Pugh B or greater)
23. Current or recent (6 months) treatment for depression, or a current diagnosis of depression or have a state of depression or suicidality at Screening
24. History of current or recent (6 months) suicidal ideation and behaviour (SIB), or history of any suicide attempt in the past 12 months.
25. History of an addiction to drugs or alcohol within 5 years prior to screening, or of alcohol or substance abuse within the past year, as determined by the Investigator

26. Current use of the following medications:, any serotonergic medication, nonselective irreversible monoamineoxidase inhibitors (MAOIs) , cytochrome P450 (CYP)1A2 inhibitors (such as fluvoxamine, ciprofloxacin, or enoxacin), cytochrome P450 (CYP) 2D6 inhibitors (bupropion, fluoxetine, metoclopramide, paroxetine, quinidine), pimozide and thioridazine, and any other medication that would be considered a safety risk for co-administration with litoxetine (See [Section 5.6.2 Prohibited Medications](#))
27. Participation in a clinical study within the month prior to Screening, or exposure to an investigational drug which has not washed out for at least 5 half-lives since its last administration, prior to Screening
28. In the opinion of the Investigator, is at risk of non-compliance with study procedures, or cannot read, understand, or complete study-related materials (including electronic diaries), particularly informed consent
29. Participation in any clinical study of an investigational drug that may affect urinary function within 3 months prior to Screening

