The BDI-II is a widely used 21-item self-report inventory measuring the severity of depression in adolescents and adults. BDI-II items are rated on a 4-point scale ranging from 0 to 3 based on the severity of each item. The maximum total score is 63. The total score derived in the eCRF will be summarized. Patients will also be classified according to the following rules: total scores of 0 to 13 indicates minimal depression, 14 to 19 indicates mild depression, 20 to 28 indicates moderate depression, and 29 to 63 indicates severe depression. A summary table will be used to describe the results at visit 1, visit 2, visit 3, visit 4, visit 5, visit 6 and visit 7. See Appendix 3 for more details on this questionnaire. A shift table will be provided to demonstrate changes in BDI-II categories from Baseline (Visit 2) to end of study (Visit 6).

The Beck Anxiety Inventory (BAI) is a widely used 21-item self-reported inventory used to assess anxiety levels in adults and adolescents. Summary tables will be used to present the total score at visit 1, visit 2, visit 3, visit 4, visit 5, visit 6 and visit 7. The total score will be computed summing up the score to each question.

The total score ranges from 0–63. The following categories for the interpretation of scores will be used: 0–7, minimal; 8–15, mild; 16–25, moderate; and 26–63, severe anxiety. A shift table will be provided to demonstrate changes in BAI categories from Baseline (Visit 2) to end of study (Visit 6).

See Appendix 4 for more details on this questionnaire.

The Pittsburgh Sleep Quality Index (PSQI) is an effective instrument used to measure the quality and patterns of sleep in adults. It differentiates “poor” from “good” sleep quality by measuring seven areas (components): subjective sleep quality (question 6), sleep latency (question 2 and 5A), sleep duration

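### BDI-II, BAI and PSQI are compared with baseline only by category shifts to Visit 6, with no change in total score and no arm difference with a confidence interval

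*SAP*

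**What the plan says.** The Protocol (Synopsis, Endpoints; section 8.7.1) names adverse events of special psychiatric interest among the primary safety endpoints: "nervousness, anxiety, panic attacks, insomnia, aggression, mania, suicidal ideation, development/worsening of depression". Protocol 6.1.1 and Appendix 2 have the BDI-II, BAI and PSQI completed at every visit, 1 to 7.

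SAP 6.8 (Psychiatric monitoring) plans four things for each scale: a listing of answers, a summary of the total or global score at Visits 1 to 7, a classification, and a shift table.

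- **BDI-II:** "The total score derived in the eCRF will be summarized". Of the bands, "total scores of 0 to 13 indicates minimal depression, 14 to 19 indicates mild depression". Then: "A shift table will be provided to demonstrate changes in BDI-II categories from Baseline (Visit 2) to end of study (Visit 6").
- **BAI:** total by visit, bands "0–7, minimal; 8–15, mild; 16–25, moderate; and 26–63, severe anxiety", and "A shift table will be provided to demonstrate changes in BAI categories from Baseline (Visit 2) to end of study (Visit 6").
- **PSQI:** global score (0 to 21) by visit, split into good and poor sleepers with poor meaning above 5, and a shift table from baseline to Visit 6.

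Under SAP 6.3, summary tables are by treatment group, with n, mean, SD, median and range. SAP 6.8 names no change from baseline in score, and no estimate, interval or test between arms, for any of the three scales.

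**The concern.** Anxiety, insomnia and worsening depression are harms this trial set out to watch in an SSRI-type drug, and the three scales are the only repeated graded measures of them. A shift table keeps only whether a subject crossed a cut-off between two visits. Movement within a band is lost, and so is a rise that came during titration, or after the taper, and was not present at Visit 6.

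What is at stake is the quality of the psychiatric safety evidence. As planned, a reader of the report would have raw means at each visit and a table of crossings. There would be no estimate of how far subjects moved from their own baseline, and no statement of how large an excess on litoxetine the data can exclude.

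**Working it through.** **1. Planned analyses side by side (SAP 6.7 and 6.8)**

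| Measure | Change from Visit 2 | Arm comparison | Other baseline comparison |
|---|---|---|---|
| Blood pressure | Visits 3 to 6 | t-test at Visit 6, with 95% CI | none |
| QT/QTc | all time points | t-test at Visit 6, with 95% CI | counts of increases over 30 and over 60 ms |
| Haematology, chemistry | mean change by arm | none | shift table |
| BDI-II, BAI, PSQI | none | none | shift table, Visit 2 to Visit 6 |

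**2. What the shift table cannot show, from the printed cut-offs**

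- BDI-II, lowest band 0 to 13: a rise of up to 13 − 0 = 13 points (scale maximum 63) is no shift, while 13 to 14, one point, is a shift.
- BAI, lowest band 0 to 7: a rise of up to 7 points (maximum 63) is no shift, while 7 to 8 is.
- PSQI, two categories: a subject starting at 6 or more is already a poor sleeper, so a rise of up to 21 − 6 = 15 points is no worsening, while 5 to 6 is.

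**3. Visits used.** There are five post-baseline visits (3, 4, 5, 6 and 7), and one enters the table. Visits 3 and 4 are the two dose-escalation visits, Visit 5 is three weeks after randomisation, and Visit 7 is the safety follow-up after the taper.

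**4. How much is hidden.** The documents give no score distribution, so this can only be bounded under assumptions. Baseline scores were simulated from a gamma distribution and a normal change was added. The SD of change was assumed to be 5 for BDI-II and BAI and 2.5 for PSQI; mean change was 0 to +5 for BDI-II and BAI and 0 to +3 for PSQI. Share of risers whose category did not worsen:

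| Scale (assumed mean baseline) | Rise of at least | Share hidden |
|---|---|---|
| BDI-II (about 3 to 7, all 13 or below) | 5 | 30–84% |
| BDI-II (same) | 10 | 5–48% |
| BAI (3 to 8) | 5 | 12–29% |
| PSQI (4 to 8) | 3 | 29–75% |

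The ranges are too wide to support any single figure.

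**5. Precision of an arm difference**

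The plan states no precision for these scales. Its only such figure, ±14% for an event rate, reproduces for the litoxetine arm at 78 × 2/3 = 52 subjects and a 50% rate (1.96 × √(0.25/52) = 13.6%; Clopper-Pearson 14.2%), but it does not bear on the scores.

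Inputs: 60 evaluable at 2:1 (SAP 3.1), so 40:20; SD of the Visit 6 total assumed 5; correlation ρ between the Visit 2 and Visit 6 totals assumed 0.5 or 0.7.

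- Unadjusted: SE = 5 × √(1/40 + 1/20) = 5 × 0.274 = 1.37, so the 95% CI is about ±1.96 × 1.37 = ±2.7 points.
- Adjusted for the Visit 2 total, the SE is multiplied by √(1 − ρ²). At ρ = 0.5, 1.37 × √0.75 = 1.19 (±2.3). At ρ = 0.7, 1.37 × √0.51 = 0.98 (±1.9).
- Range over the assumed SD: at SD 4 the three SEs are 1.10, 0.95 and 0.78; at SD 7 they are 1.92, 1.66 and 1.37.
- The stated 30% dropout from 78 leaves 78 × 0.7 = 54.6 rather than 60. At 36:18 and SD 5 the SEs are 5 × √(1/36 + 1/18) = 1.44, then 1.25 and 1.03.
- A plain difference in change scores multiplies the unadjusted SE by √(2(1 − ρ)). That is 1 at ρ = 0.5 (no gain) and 0.775 at ρ = 0.7 (1.06), which is why the adjusted estimate is preferred to a t-test on change.

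**The case against.** The other side has several good points.

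- **The endpoint is the adverse event, not the score.** Psychiatric TEAEs are tabulated by arm with severity and Clopper-Pearson intervals (SAP 6.7, item 2). Changes in blood pressure and ECG are listed primary endpoints (SAP 2.3, items 5 and 6); changes in these scores are not, so the comparison is not quite like with like. This stands. But an adverse event has to be reported. The documents set no BDI-II, BAI or PSQI score that generates one, and only the C-SSRS has a stated consequence (Protocol 6.1.2.3). The scales are therefore partly independent evidence.
- **Totals are shown by arm at each visit.** A reader might infer that a steady worsening on litoxetine would go unseen. The documents do not support that: rising litoxetine means would appear beside placebo, and in a randomised trial that is a valid comparison. What is missing is the paired change and the interval for the difference.
- **Dropout is not the argument.** Withdrawn subjects undergo the Visit 6 procedures, including these scales (Protocol 7.1.6; Appendix 2, note 4). An ANCOVA of the Visit 6 total also uses only subjects who have one, so it does not cure dropout.
- **The safety section is mainly descriptive, and the scores may be skewed and bound at the floor.** This also stands. It argues for labelling the adjusted difference as supportive and checking it, not for leaving out the change.

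**Conclusion.** The gap is real and can be read directly from SAP 6.8: category shift from Visit 2 to Visit 6 is the only planned comparison with baseline for the three scales, with no change in score and no arm difference with an interval. The size of the blind spot in that table follows from the cut-offs alone: up to 13 BDI-II points, 7 BAI points, or any PSQI rise from 6 upward, plus four of the five post-baseline visits.

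Two stronger readings should be resisted. A reader might infer that most worsening will be tabulated as no change. That needs score distributions the documents do not give; under the assumed ones it fails for BAI rises of 5 or more and for BDI-II rises of 10 or more. A reader might also infer that the population starts at the bottom of all three scales because depressed subjects are excluded. Exclusion 23 covers "a current diagnosis of depression or have a state of depression or suicidality at Screening". It bears on the BDI-II only and sets no BDI-II limit, and there is no general exclusion for anxiety or poor sleep.

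This is a cheap improvement in sensitivity and precision, not a flaw that invalidates the safety analysis. The standard errors are illustrations that rest on the assumed SD and correlation.

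**What to change.** In SAP 6.8, for the BDI-II, BAI and PSQI totals:

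1. Summarise within-subject change from Visit 2 by arm at each post-baseline visit, including Visit 7.
2. Summarise each subject's largest post-baseline increase by arm.
3. Add, as a supportive estimate, an ANCOVA of the Visit 6 total on arm and the Visit 2 total, reporting the adjusted difference and 95% CI. State that it carries no multiplicity-controlled claim, and check it against skewed, floor-bound scores, for example with a rank-based or bootstrap interval.
4. Keep the shift tables and the totals by visit.

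The wording should be fixed before unblinding. The cost is a short SAP text change and a few tables from scores already in the eCRF; nothing new is collected and no clinical rule changes. The downside is some extra output and supportive contrasts in a mainly descriptive safety section.

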6.9 Efficacy Analyses

Efficacy will be assessed by the number of urinary incontinence episodes. There is only one hypothesis so there will be no adjustment for multiplicity.

The efficacy analysis will be performed on the ITT and PP populations.

There will not be an adjustment for multiple comparisons for these efficacy analyses.

Baseline for all efficacy endpoints will be defined as the last week of the Screening Placebo Run-In Period (Visit 2). The final measurement (endpoint) will be defined as Week 8 (Visit 6).

1. Percentage change from end of the Screening Placebo Run-In Period to Week 8 in the number of incontinence episodes in a week

The efficacy analysis planned is an analysis of covariance model (ANCOVA). Percentage change in the number incontinence episodes/week is the response variable. The factor variables will be dose and centre. If the center effect is significant, summary statistics will be presented to describe the effect. The covariate will be end of the Screening Placebo Run-In Period episodes of incontinence.

The percentage change, $\%UIE_i$, for subjects in each arm, is expressed as the ratio of the total number of urinary incontinence episodes in a week between final measurement ($UIE_{i,end}$) and baseline ($UIE_{i,base}$)

$$\%UIE_i = \frac{UIE_{i,end}}{UIE_{i,base}}$$

Since percentage change from baseline does not have the properties of additivity and symmetry, it will be log-transformed, and the response variable will be the natural logarithm of the ratio of Week 8 (Visit 6) to Baseline, as shown below:

$$\log(\%UIE_i) = \log\left(\frac{UIE_{i,end}}{UIE_{i,base}}\right)$$

The hypothesis test being conducted is as follows:

$$\begin{aligned} H_0: \log(\%UIE_{\text{Litoxetine}}) - \log(\%UIE_{\text{Placebo}}) &= 0 \\ H_1: \log(\%UIE_{\text{Litoxetine}}) - \log(\%UIE_{\text{Placebo}}) &\neq 0, \end{aligned}$$

This is equivalent to testing the hypothesis:

$$H_0: \log\left(\frac{\%UIE_{Litoxetine}}{\%UIE_{Placebo}}\right) = 0$$

The result of the ANCOVA model will be expressed as log % and then back transformed to percentage change. Therefore, H_0 can be interpreted as:

$$H_0: \frac{\%UIE_{Litoxetine}}{\%UIE_{Placebo}} = 1$$

This makes the actual statistics:

$$\delta = \log(\%UIE_{Litoxetine}) - \log(\%UIE_{Placebo}) = \log\left(\frac{\%UIE_{Litoxetine}}{\%UIE_{Placebo}}\right)$$

When back-transformed, this is expressed as follows:

$$\Delta = \exp\left(\log\left(\frac{\%UIE_{Litoxetine}}{\%UIE_{Placebo}}\right)\right) = \frac{\%UIE_{Litoxetine}}{\%UIE_{Placebo}}$$

$\%UIE_i$ is the ratio of the total number of urinary incontinence episodes in a week at endpoint (Visit 6) ($UIE_{i,end}$) to the total number of urinary incontinence episodes in a week at baseline ($UIE_{i,base}$) for arm i , with i equal to Litoxetine or Placebo.

An ANCOVA will be performed to compare δ to 0; the test will provide an appropriate p-value with a significance level alpha equal to 0.05. This p-value will be computing the probability of observing a difference among arms.

Numbers of incontinence episodes equal to 0 (not missing) will be imputed as 0.4 to allow for the log transformation.

2. Absolute change from end of the Screening Placebo Run-In Period to Week 8 in the number of incontinence episodes/24 hours (daily average)

The analysis planned is an analysis of covariance model (ANCOVA). Absolute change in the total number of incontinence episodes/24 hours is the response variable. The factor variables will be dose and centre. The covariate will be end of the Screening Placebo Run-In Period episodes of incontinence.

Number of incontinence episodes/24 hours will be computed as Total Number of incontinence episodes recorded during the 7-day period and entered in the eCRF divided by 7, as defined in Section 5.4.

The hypothesis test being conducted is as follows:

$$H_0: \Delta UIE_{Litoxetine} - \Delta UIE_{Placebo} = 0$$
$$H_1: \Delta UIE_{Litoxetine} - \Delta UIE_{Placebo} \neq 0$$

Where ΔUIE_i is the absolute change, for subjects in arm i , in the number of incontinence episodes/24 hours as defined above from baseline ($UIE_{i,base}$) to the final measurement ($UIE_{i,end}$):

$$\Delta UIE_i = UIE_{i,end} - UIE_{i,base}.$$

Where i goes from 1 to 2 and it represents the 2 arms: Litoxetine and Placebo.

3. Proportion of subjects who become continent at Week 8

A subject is defined as continent if s/he has no incontinence episodes at Visit 6 (Week 8). Frequencies will be used to describe the proportion of subjects who are continent at Week 8. The proportion will be computed on the total number of subjects for each arm at baseline. The category Missing will be included in the analysis, to consider subjects who do not attend the visit or who have missing values for that visit.

Differences between groups will be evaluated using Chi-square test or Fisher's exact test (if more than 20% of the cells in a contingency table have counts less than 5).

4. Change from end of the Screening Placebo Run-In Period to Week 8 in the number of incontinence pads used per week

The analysis planned is an analysis of covariance model (ANCOVA). Absolute change in the number of incontinence pads used per week is the response variable. The factor variables will be dose and centre. The covariate will be the number of pads used at the end of the Screening Placebo Run-In Period.

Number of incontinence pads used per week will be derived for the eCRF, as defined in Section 5.4.

The hypothesis test being conducted is as follows:

$$\begin{aligned} H_0: \Delta \text{Pads}_{\text{Litoxetin}} - \Delta \text{Pads}_{\text{Placebo}} &= 0 \\ H_1: \Delta \text{Pads}_{\text{Litoxetin}} - \Delta \text{Pads}_{\text{Placebo}} &\neq 0 \end{aligned}$$

Where ΔPads_i is the absolute change, for subjects in arm i , in the number of incontinence pads used per week from baseline ($\text{Pads}_{i,\text{base}}$) to the final measurement ($\text{Pads}_{i,\text{end}}$):

$$\Delta \text{Pads}_i = \text{Pads}_{i,\text{end}} - \text{Pads}_{i,\text{base}}.$$

Where i goes from 1 to 2 and it represents the 2 arms: Litoxetin and Placebo.

5. Percentage change from end of the Screening Placebo Run-In Period to Week 8 in the number of nocturia episodes in a week

The analysis planned is an analysis of covariance model (ANCOVA). Percentage change in the total number of nocturia episodes in a week is the response variable. The factor variables will be dose and centre. The covariate will be end of the Screening Placebo Run-In Period episodes of incontinence.

The number of nocturia episodes in a week is the total number of nocturia episodes recorded over the 7-day period and entered in the eCRF, as defined in Section 5.4.

The analysis will be carried out as described in section 6.9 point 1.

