Statistical Methods:	
Study Populations:
 
The Safety Population (SP) is defined as all subjects who are randomised and receive the study drug, and undergo at least 1 visit.
 
The intent-to-treat (ITT) population includes all subjects who are randomized
 
The modified intent-to-treat (mITT) population includes all subjects who are randomized, receive at least 1 dose of study drug, and provide an end of study primary efficacy endpoint.
 
The Per Protocol (PP) population is defined as those subjects who meet the ITT criteria and have completed the trial without a major protocol violation.
 
The efficacy analysis will be performed on the ITT, mITT, and PP populations. The primary efficacy analysis will be performed on the ITT population with the analysis of the primary end-point on the mITT and PP populations as part of the secondary efficacy analysis.
 
The efficacy analysis planned is a mixed effects model with repeated measure (MMRM). Percent reduction in incontinence episodes as the response variable is the first efficacy endpoint. The factor variable will be dose and centre. The covariate will be end of the Screening Placebo Run-In Period episodes of incontinence. Visits within subjects will provide the random effects of the mixed model. There is only one hypothesis so there will be no adjustment for multiplicity. Further efficacy analysis will be conducted similarly, with appropriate baseline measures. There will not be an adjustment for multiple comparisons for these secondary endpoint analyses.
 
Safety Analyses: Safety data will be presented and analysed using the Safety Population.
 
 Serious adverse events (SAEs) will be listed and summarised in a table, including a description of each event, the time to onset, the severity, and the relationship to trial drug. All AEs (excluding SAEs) will be listed, and their time to onset, frequency, severity, and relationship to the trial drug will be tabulated by treatment. Adverse events that occur before the time of the first treatment with the trial drug will be considered a non-treatment- emergent AE (non-TEAE), and all AEs that occur after the time of the first treatment with trial drug will be considered TEAEs. Non-TEAEs will be summarised separately from TEAEs. Adverse Events of Special Interest (AESI) include urinary retention, psychiatric adverse events (nervousness, anxiety, panic attacks, insomnia, aggression, mania, suicidal ideation, development/worsening of depression) and withdrawal symptoms will be specifically summarized.

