2.4 Secondary Endpoints(s)

Efficacy:

1. Percentage change from end of the Screening Placebo Run-In Period to Week 8 (Visit 6) in the number of incontinence episodes in a week
2. Absolute change from end of the Screening Placebo Run-In Period to Week 8 (Visit 6) in the number of incontinence episodes/24 hours (daily average)
3. Proportion of subjects who become continent at Week 8 (Visit 6)
4. Change from end of the Screening Placebo Run-In Period to Week 8 (Visit 6) in the total number of incontinence pads used per week
5. Percentage change from end of the Screening Placebo Run-In Period to Week 8 (Visit 6) in the number of nocturia episodes in a week.

3. Study Design

This is a Phase 1/2a, double-blind, randomised, placebo-controlled, parallel-group study in subjects 18 to 70 years old diagnosed with UI.

The study will include a 2-week, single-blind (subject blind) Screening Placebo Run-In Period and an 8-week double-blind Treatment Period. The Treatment Period will be followed by a 1 week Dose-tapering Period and subjects will return to the clinic for a safety Follow up Visit 4 weeks after treatment is completed. This provides a total study duration of 15 weeks. No interim analysis is planned.

All subjects will enter the Screening Placebo Run-In Period during which eligibility will be assessed and single blind placebo run-in medication will be provided. In the latter half of this period, the subject will complete 7 days of bladder diary to capture incontinence events and pad usage. Subjects who continue to meet eligibility criteria after the Screening Placebo Run-In period, will enter the Treatment Period and be randomly assigned (2:1) to receive study drug (litoxetine10 mg, 20 mg, 30mg) or matching placebo BID.

Litoxetine or placebo treatment will be provided with dose titration, starting with 10 mg BID for 1 week, escalated to 20 mg BID for 1 week, and subsequently escalated to 30 mg BID for 6 weeks' duration (for a total treatment period of 8 weeks).

If the subject does not tolerate the last dose level escalation (i.e. cannot tolerate 30 mg BID), the dose can be reduced to the previous dose level (20 mg BID). If the patient does not tolerate the lower dose level (20 mg BID) s/he will be discontinued from the study. After 8 weeks of treatment, doses will be reduced by 50% over 1 week to taper off treatment. A safety follow up visit will occur 4 weeks after treatment is permanently stopped (total study duration 15 weeks).

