Categorical variables will be summarised by using frequency distributions and percentages.

For all analyses, hypothesis testing will be carried out at the alpha = 0.05 level (two-sided) when comparing treatments. P-values will be rounded to three decimal places. Statistical significance will be declared if the rounded p-value will be less than or equal to 0.05.

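### SAP 6.9 waives multiplicity adjustment because there is a single hypothesis, yet it tests five efficacy endpoints in two unranked populations and SAP 6.3 lets each be declared significant at 0.05

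*SAP*

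**What the plan says.** **SAP, reason for no adjustment (6.9).** "There is only one hypothesis so there will be no adjustment for multiplicity". Shortly afterwards, without a reason: "There will not be an adjustment for multiple comparisons for these efficacy analyses".

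**SAP, what is tested (2.4 and 6.9).** There are five endpoints:

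1. percentage change in weekly episodes, analysed as a log ratio
2. absolute change in episodes per 24 hours
3. proportion continent
4. change in weekly pad use
5. percentage change "in the number of nocturia episodes in a week"

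Endpoints 1, 2 and 4 each have their own null and alternative hypotheses. Endpoint 5 follows the method of endpoint 1. For endpoint 3, "Differences between groups will be evaluated using Chi-square test or Fisher's exact test".

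**SAP, populations (6.9).** "The efficacy analysis will be performed on the ITT and PP populations". Neither is named as leading.

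**SAP, decision rule (6.3).** For all analyses, "hypothesis testing will be carried out at the alpha = 0.05 level (two-sided) when comparing treatments", and "Statistical significance will be declared if the rounded p-value will be less than or equal to 0.05".

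**Protocol (Synopsis and 8.8.2).** Percent reduction in episodes is named as the leading efficacy endpoint, and the single-hypothesis sentence follows directly from it. On populations, the Synopsis says: "The primary efficacy analysis will be performed on the ITT population with the analysis of the primary end-point on the mITT and PP populations". The remaining endpoints are treated separately, as secondary and unadjusted.

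**The concern.** The reason given for not adjusting does not describe the section it stands in. In the protocol the sentence could be read as applying to one named endpoint in a leading population. In SAP 6.9 it stands over five tested endpoints in two populations, with no statement that one test decides.

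Exploratory efficacy analyses need no familywise control if they are reported as estimates with nominal p-values. SAP 6.3 goes further and provides for significance to be declared on every comparison. The trial report could then call efficacy significant on whichever endpoint or population crossed 0.05, and cite the SAP for it. The sample size rests on the precision of a safety event rate, with no efficacy power stated, so an isolated p-value below 0.05 would be easy to over-read.

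**Working it through.** **The plan's own figures.** The documents give no familywise error rate and no efficacy power. The only design figure is the ±14% half-width for a 50% safety event rate in the treatment arm. With 78 × 2/3 = 52 subjects, 1.96 × √(0.25/52) = 13.6% (Clopper-Pearson 14.2%), so it reproduces for the randomised litoxetine arm. It has no bearing on the efficacy tests.

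**Inputs from the documents.** Two-sided 0.05 per test; p rounded to three decimals before comparison, so any p below 0.0505 passes; five endpoints; two populations; about 78 randomised 2:1 (52:26); 60 evaluable.

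**Assumed inputs.** Correlation between endpoint test statistics: 0.3 to 0.9. Correlation between the ITT and PP statistics for the same endpoint: 0.80 to 0.95. For a random subset the latter is about the square root of the fraction retained: √(60/78) = 0.88, and √0.90 = 0.95 if PP is 90% of ITT.

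**Reference values under independence.**
- One test: 5.0% in either direction, 2.5% favouring litoxetine.
- Five tests, either direction: 1 − 0.95⁵ = 22.6%.
- Five tests, favouring litoxetine: 1 − 0.975⁵ = 11.9%.
- At the effective level 0.0505 these two become 22.8% and 12.0%.

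Independence overstates the case, because endpoints 1, 2 and 3 all come from the same diary count.

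**Correlated normal model** (400,000 draws, per-test level 0.0505, no drug effect). Chance of at least one declared difference:

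| Endpoint correlation | ITT, either direction | ITT, favouring litoxetine | ITT + PP, either direction | ITT + PP, favouring litoxetine |
|---|---|---|---|---|
| 0.3 | 21% | 11% | 26–31% | 13–16% |
| 0.5 | 18% | 9% | 23–27% | 12–14% |
| 0.7 | 15% | 7% | 19–22% | 9–11% |
| 0.9 | 10% | 5% | 13–15% | 6–8% |

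The ITT + PP ranges run from an ITT–PP correlation of 0.95 (lower) to 0.80 (higher). At 0.85, with endpoint correlations 0.3, 0.5 and 0.7, the figures are 30%, 26% and 21% in either direction, and 15%, 13% and 11% favouring litoxetine.

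**Data-level simulation** (6,000 null trials in each of five scenarios; 52:26; simulated weekly counts; the SAP's endpoint definitions, with zeros replaced by 0.4; its chi-square or Fisher rule; rounded p; PP a random 77% or 90% of ITT; no centre term and no missing ITT data):
- Five ITT tests: 12.6–14.1% in either direction, 6.0–7.6% favouring litoxetine.
- ITT plus PP: 15.8–20.1% in either direction, 7.5–10.6% favouring litoxetine.

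These lie inside the normal-model ranges. Part of the reason for the lower values is that the continence test rejects well below 5% (0.1–3.7% in ITT).

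**Rounding alone.** The per-test level moves from 5.00% to 5.05%.

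**After the fix.** One test, endpoint 1 in ITT: 5.0% two-sided, about 2.5% favouring litoxetine.

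**The case against.** The best defence is that nothing confirmatory is at stake. Safety is primary, both documents describe efficacy as something to explore, no success criterion hangs on an efficacy p-value, and SAP 6.9 says openly that there is no adjustment. There are also signs of which test was meant to lead. Percentage change is listed first in SAP 2.4 and 6.9, SAP 1.6 speaks of the efficacy endpoint in the singular and identifies it as percentage change, and the 0.05 level is restated in 6.9 only for that endpoint. SAP 1.5, which lists departures from the protocol, announces the loss of mITT but no change to the priority of ITT.

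Much of this stands, and it limits the point. It does not rescue the stated reason, which is wrong for a section with five tested endpoints. Nor does it remove the SAP 6.3 rule that lets significance be declared on all of them.

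Stronger readings are tempting, but the documents do not support them:

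- *A false efficacy claim has a 15–30% chance.* A range of that size counts differences in either direction, including placebo doing better. An efficacy claim needs a result favouring litoxetine, which is about half as likely.
- *There are twenty routes to a claim:* 5 × 2 in 6.9, six in 6.9.1 and four in 6.9.2. Item 6 of 6.9.1 is endpoint 2 multiplied by 7 and gives the same p-value. Item 5 is the endpoint 1 ratio with the sevens cancelling, apart from the handling of zeros. The rest are labelled sensitivity or exploratory, and the 6.9.2 analyses also depend on data variability and subgroup size.
- *The SAP made ITT and PP co-equal.* It is silent on their ranking; it does not say that they are equal.
- *The rounding rule inflates error materially.* It adds 0.05 percentage points per test.

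**Conclusion.** The point holds as an error of premise and decision rule. SAP 6.9 claims one hypothesis, tests five endpoints in two unranked populations, and under SAP 6.3 may declare any of them significant. The protocol's order, which would have given the sentence a meaning, is not carried into SAP 6.9.

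With no drug effect, the chance of at least one declared difference in either direction is about 10–21% for the five ITT tests and about 13–30% with PP added (31% at the most extreme combination examined). The chance of one favouring litoxetine is about 5–11% and 6–16% respectively, roughly two to six times the 2.5% of a single two-sided test.

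The contradiction in the text is certain. The size is less so: it depends on assumed correlations and on the share of ITT subjects who enter PP, and the upper ends need PP counted as a separate route to a declaration. Because efficacy is exploratory and the lack of adjustment is disclosed, the consequence is a risk of over-reading and does not invalidate the trial's design.

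**What to change.** In SAP 6.3 and 6.9, restore the protocol's order. Confine the single-hypothesis sentence and the declaration rule with text such as:

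*For efficacy, statistical significance will be declared only for endpoint 1 (log ratio of weekly incontinence episodes) in the ITT population, at two-sided p ≤ 0.05. All other efficacy p-values are nominal, are presented with 95% confidence intervals and will not be described as significant. PP results are supportive.*

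As a minor tidy-up, apply the 0.05 threshold to the unrounded p-value wherever the rule appears, in SAP 6.3 and in the blood pressure comparison in SAP 6.7. A p-value of 0.0504 would then no longer be called significant while its 95% interval includes no effect.

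Cost: SAP wording only. Sample size, data collection and the power of endpoint 1 are unaffected. The other efficacy endpoints can no longer be called significant. If the sponsor wants to keep that option, a Bonferroni level of 0.05/5 = 0.01 for each ITT test would hold the familywise rate at or below 5%, but at a loss of power for endpoint 1.
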